3. STATISTICAL METHOD

3.1 General considerations

The statistical analysis will be performed by the statistician of the Biostatistics Department at Ramón y Cajal Hospital, under the supervision of the Coordinating Investigator. The strategy for the design and the analysis will be made in compliance with the CONSORT statement (<http://www.consort-statement.org/>).

All statistical analyses will be carried out with SAS (SAS Institute, Cary, NC, USA) and R (R Core Team. R Foundation for Statistical Computing, Vienna, Austria) softwares. A p-value inferior to 0.05 will be considered as statistically significant unless stated otherwise.

3.2 Missing data

Missing data won't be replaced, and analysis will be made on all evaluable patients. In addition, sensitivity analyses will be made on the primary and secondary end points using worst case and/or multiple imputations (see 3.5.3). Missing or incomplete data for survival analyses will be managed by censored data analyses.

3.3 Protocol deviations

All protocol deviations will be listed and summarized in a blinded manner before the database lock preliminary to the final statistical analysis. Deviations will be classified as minor or major. The process will enable the population inception for the analyses (global, randomized, per-protocol).

The description of the protocol deviations may be found in section 7 of the SAP.

3.4 Baseline demographics and clinical characteristics

Baseline characteristics will be summarized by strategies on the randomized population. Only descriptive analyses will be provided (no inferential statistics).

Results will be presented as mean \pm one standard deviation if the variable follows a normal distribution and median [interquartile range] in case of other distribution. For the qualitative or categorical quantitative variables, results will be presented as numbers (proportions in %).

3.5 Hypotheses and statistical methods

3.5.1 Hypothesis

The primary aim of the trial is to demonstrate superiority in the intent-to-treat analysis of an active search for PE over usual care with regard to primary end point as the composite of death from any cause, non-fatal (recurrent) symptomatic VTE, or readmission for COPD exacerbation within 90 days after enrollment (90daycomposite).

The null and alternative hypotheses are as follows:

$$H_0: 90\text{daycomposite}_{\text{intervention}} = 90\text{daycomposite}_{\text{control}}$$

$$H_1: 90\text{daycomposite}_{\text{intervention}} \neq 90\text{daycomposite}_{\text{control}}$$

3.5.2 Statistical analysis

The principal analysis of the primary and secondary end points will be performed on the evaluable patients from the randomized population with application of the intent-to-treat principle. In addition, safety analyses will be performed in the safety analysis set, which included all the patients in the control arm, and all the patients in the intervention arm who had received a D-dimer testing. The alpha level of the two-sided test is set to 0.05. The primary efficacy and safety end points will be analyzed by means of a two-sided chi-square test of proportions. The results for the primary end points will be also stratified according to center (4). Secondary end points will not be adjusted for multiplicity, and therefore these results should not be used to infer intervention

effects (5). Kaplan-Meier survival curves until 90 days after randomization will be compared with a log-rank test. For each end point, results will be presented as the relative risk (intervention:control) for percentages and difference (intervention-control) for means, and its 95% confidence interval (**CI**).

Cost-effectiveness will not be analyzed for the main presentation of the SLICE study but will be performed later as an ancillary study.

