Control group: All included patients will undergo standard clinical management of their exacerbations, as deemed appropriate by the attending physician.

Criteria for efficacy:

Primary end point

- Clinical composite endpoint of all-cause mortality or venous thromboembolism recurrence or need for COPD readmission within 90 days.

Secondary end points

- All-cause mortality within 90 days.
- Venous thromboembolic recurrence within 90 days.
- Need for COPD readmission within 90 days.
- Length of hospital stay.

Criteria for safety:

Primary end point

- Major bleeding within 90 days.

Secondary end points

- Clinically relevant non-major bleeding within 90 days.
- Serious adverse events within 90 days.

Statistical analysis: Intent-to-treat (ITT) analysis on superiority of an active strategy for the diagnosis and treatment of PE in patients with unexplained exacerbations of COPD requiring hospital admission.

Primary criteria

The primary ITT analysis on the primary end points will be carried out by a two-sided chi-square test on proportions. In addition, the 95% confidence interval on the relative risks will be presented.

Secondary efficacy criteria

The secondary ITT analysis on the secondary efficacy end points will be carried out by a two-sided chi-square test on proportions. In addition, the 95% confidence interval on the relative risks will be presented. The survival status during 90 days follow-up will be analyzed by showing Kaplan-Meier curves, and management differences will be compared by means of log-rank test.

Secondary safety analysis

Safety end points will be tabulated by management group. All (dichotomized) end points will be analyzed by chi-square test on proportions, and the 95% confidence interval on the relative risks will be presented. In addition, continuous safety monitoring will be done by the Data and Safety Monitoring Board.

Interim analysis

Interim analysis will be made by the Data Center after recruitment of 50% of the total number of patients. These analyses will be made in order to allow sample size reassessment or early stop of the trial for efficacy or futility.

TABLE OF CONTENTS	Page
ABBREVIATIONS	15
1. BACKGROUND	16
1.1 Study justification	16
1.2 Hypothesis	17
1.3 Objectives	17
2. METHODOLOGY	20
2.1 Design	20
2.2 Setting	20
2.3 Study subjects	21
2.4 Randomization	22
2.5 Study procedures	22
2.6 Criteria for termination of the trial	23
2.7 Definition of study end points	23
2.8 Surveillance and follow-up	28

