The primary ITT analyses will be carried out by the chi square test on proportions, or the Fisher exact test. In addition, the corresponding 95% on the relative risks will be presented.

Safety analyses

The secondary ITT analyses will be carried out by the chi square test on proportions, or the Fisher exact test. In addition, the corresponding 95% on the relative risks will be presented.

Patient accountability

Disposition of patients, patient status and patients excluded from ITT will be summarized by group (intervention and control). Descriptive statistics for primary reason for patient's withdrawal will be also presented by group (intervention and control) as well as a list of these patients sorted by group (intervention and control).

Drop-outs

Reasons for drop-outs in each group (intervention and control) will be displayed. A detailed list of drop-out patients will also be provided.

Baseline characteristics

Baseline characteristics will be tabulated and comparability / differences between the treatment groups will be examined by means of descriptive statistics.

Subgroup analysis

The following subgroup analyses will be carried out: age (<75 versus ≥ 75), sex (women versus men), COPD severity ($FEV_1 > 80\%$, $50\% \leq FEV_1 < 80\%$, $30\% \leq FEV_1 < 50\%$, and $FEV_1 < 30\%$), hospital size (<300 beds versus ≥ 300 beds) and season (autumn, winter, spring, summer).

Interim analysis

We will conduct an interim analysis after recruitment of 50% of the study population. To preserve an overall type I error rate of 0.05 for the entire trial, the O'Brien-Fleming type boundary (alpha of 0.005) will be used for early trial stoppage. Futility will be assessed with conditional power, an approach that quantifies the probability of rejecting the null hypothesis of no effect. Stopping rule for futility will be based on a conditional power less than 20%.

Handling of missing data

Missing data won't be replaced, and analysis will be made on all evaluable patients. If necessary, sensitivity analyses will be made on the primary and secondary end points using worst case and/or multiple imputations (see 3.5.3). Missing or incomplete data for survival analyses will be managed by censored data analyses.

Sample size

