2.2 Sample size and power consideration

Previous studies have shown short-term rates of death, thromboembolic events, or readmission of approximately 40% at day 90 among patients who required hospital admission because of an exacerbation of COPD (1, 2). An estimated 355 participants will be needed in each trial group to detect a clinically important 10% absolute reduction in the primary outcome (i.e., from 40% to 30%) with 80% power at 5% significance level. The 10% reduction was based on consultation with primary and secondary care colleagues (general practitioners and pulmonologists) who considered a 10% reduction to be small but clinically important. Since an interim analysis showed that 3% of patients were lost to follow-up, the Steering Committee anticipated a 5% loss to follow-up. This inflated each study group to 373 patients, giving 746 patients in total.

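### The SAP tests the primary efficacy end point at the full 0.05, although the protocol allots 0.005 to an interim efficacy look within an overall 0.05

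*SAP*

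**What the plan says.** Protocol section 2.10 (Interim analysis) plans one interim analysis after 50% of recruitment: "To preserve an overall type I error rate of 0.05 for the entire trial, the O'Brien-Fleming type boundary (alpha of 0.005) will be used for" stopping the trial ahead of schedule. It adds a futility rule at conditional power below 20%, without saying whether the rule is binding or which effect the conditional power assumes. The abbreviated protocol gives the purpose of the look: "These analyses will be made in order to allow sample size reassessment or early stop of the trial for efficacy or futility".

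The SAP has no interim boundary, no alpha spending and no final nominal level. Section 3.1 says "A p-value inferior to 0.05 will be considered as statistically significant unless stated otherwise", and nothing else is stated for the primary efficacy end point. Section 3.5.2 says "The alpha level of the two-sided test is set to 0.05" and reports each relative risk "and its 95% confidence interval". The SAP mentions an interim only in section 2.2, where the sample size is explained: "Since an interim analysis showed that 3% of patients were lost to follow-up".

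**The concern.** The protocol's commitment covers the whole trial: "To preserve an overall type I error rate of 0.05 for the entire trial". If 0.005 may be used at the interim, the final test cannot also use the full 0.05 without exceeding that total. An O'Brien-Fleming type boundary implies a final level just below 0.05, but neither document writes it down, and the SAP's decision rule is p below 0.05.

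At stake is the trial's main claim when the result is borderline. A final p-value between about 0.048 and 0.05 would be a success under the SAP and a failure under the protocol's boundary. If the level is unsettled when the data are unblinded, choosing between them becomes a data-driven decision.

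**Working it through.** **Inputs.** Interim two-sided level 0.005 at 50% recruitment, and overall level 0.05 (protocol 2.10). Final two-sided level 0.05 and chi-square test (SAP 3.5.2). Event rates 40% and 30%, 80% power, 355 per arm, 373 after inflation, 746 in total (SAP 2.2).

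**1. The plan's own sample size.** With pooled variance under the null hypothesis:

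n = [1.960 × √(2 × 0.35 × 0.65) + 0.842 × √(0.40 × 0.60 + 0.30 × 0.70)]² / 0.10² = 355.9, so 356 per arm.

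The unpooled formula gives 353.2, so 354. The stated 355 lies between the two, and 355 × 1.05 = 372.75 gives 373. The sample size was therefore computed at the full two-sided 0.05, with no allowance for the interim look.

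**2. Overall error with 0.005 and then 0.05.** Under the null hypothesis the two test statistics are bivariate normal with correlation √t, where t is the information fraction. Futility is treated as non-binding. The critical values are 2.807 and 1.960.

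Overall error = 1 − P(|Z₁| < 2.807 and |Z₂| < 1.960)

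At t = 0.5 this is 0.0519. The simple sum 0.005 + 0.05 = 0.055 is only an upper bound, because the two looks share data.

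**3. Final level that gives exactly 0.05.** Solve 1 − P(|Z₁| < 2.807 and |Z₂| < c) = 0.05 for c.

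| Information fraction at the look | Overall error if final level is 0.05 | Final c | Final two-sided level | Matching CI |
|---|---|---|---|---|
| 0.50 (as planned) | 0.0519 | 1.977 | 0.0481 | 95.2% |
| 0.634 (assumption) | 0.0511 | 1.969 | 0.0489 | 95.1% |

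The second row assumes that the look came at half of an earlier total based on 75% evaluable. That total would be 2 × 355 / 0.75 ≈ 947, half of it is 473, and 473 / 746 = 0.634. The documents give the 75% (protocol, summary of changes) but not the earlier total. If information lagged behind recruitment, so that t = 0.40, the overall error would be 0.0525 and the final level about 0.047.

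As a cross-check, the classical two-look O'Brien-Fleming pair is 0.0052 and 0.0480, and Lan-DeMets spending of that type gives 0.0056 and 0.0478.

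**4. Power at the corrected level, 40% against 30%.** The drift at 355 per arm is 0.10 / √(0.45 / 355) = 2.809 (unpooled) or 0.10 / √(0.455 / 355) = 2.793 (pooled).

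| Evaluable per arm | Look at 50% | Look at 63% |
|---|---|---|
| 355 | 79.4% to 79.9% | 79.6% to 80.1% |

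The ranges cover the two variance formulas and the final chi-square test taken alone. For comparison, a single final test at 0.05 with 355 per arm has 79.9%. With the observed 3% loss, 373 × 0.97 ≈ 362 are evaluable per arm, and power is 80.2% to 80.8% across both timings. No change of sample size is needed.

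**5. A result where the rule decides.** Take 138/355 events (38.9%) under usual care and 113/355 (31.8%) under the active strategy. The pooled proportion is 251/710 = 0.3535.

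z = (0.3887 − 0.3183) / √(0.3535 × 0.6465 × 2 / 355) = 1.963, so p = 0.0497.

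This passes at 0.05 and fails at both 0.0481 and 0.0489.

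**The case against.** The strongest objection concerns futility. If the trial must stop when conditional power is below 20%, some false positives at the final analysis are removed. With conditional power taken under the current trend and the rule applied in both directions (both assumptions), the overall error with a final 0.05 is about 0.043 at t = 0.5 and 0.044 at t = 0.634. A plan with a binding rule would therefore not exceed 0.05. This stands as arithmetic, but the protocol does not call the rule binding and does not define the conditional power. Credit for futility is not normally taken on those terms, so the figure of 0.0519 depends on the non-binding convention.

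Second, the interim may never have compared the arms. The only interim results reported are the loss to follow-up and the resulting change in the evaluable rate. If there was no comparison, no alpha was spent and 0.05 is correct. The documents do not say either way, and the plan as written spends it.

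Third, the SAP's 0.05 could be read as the overall level. Section 3.5.2 attaches it to the test itself, however, and section 3.1 applies it to the p-value. Even on the generous reading, the final threshold is missing.

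Fourth, the effect is tiny. The chance that the final p-value falls between 0.0481 and 0.05 is about 0.2% under the null hypothesis and 0.5% under the design effect, and the example above was chosen to fall there. This stands, and it limits the weight of the point.

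**Conclusion.** The concern holds. The protocol promises 0.05 for the entire trial and allots 0.005 of it to an interim efficacy test, while the SAP's final decision rule uses the full 0.05 and neither document gives a reduced level. With futility non-binding, the overall error is 0.0519 for a look at half information, and 0.0511 if the look came at about 63%. The correct final level is 0.0481 or 0.0489 respectively.

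The size rests on three things the documents leave open: whether the arms were compared, whether futility was binding, and the information fraction at the look. The wording of the protocol's summary of changes may also imply more than one look. The numerical effect is small and the conclusion changes only for a p-value in a narrow band, but the threshold for the primary claim should be corrected before database lock.

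**What to change.** In SAP sections 3.1 and 3.5.2, set the final two-sided level for the primary efficacy end point to 0.048 (0.0481 at 50% information), or to the value that the same 0.005 boundary gives at the actual information fraction (about 0.049 at 63%). Report the primary relative risk with the matching interval, 95.2% or 95.1%. In section 2.2, restate power at 355 evaluable per arm at the chosen level. By the pooled formula that matches the chi-square test it is about 79.5% at a 50% look and 79.6% at a 63% look.

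Record the number and timing of looks, whether the arms were compared, the effect assumed for conditional power, and whether the futility rule was binding. If no between-arm comparison was made at any look, state that and keep 0.05.

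The cost is SAP wording before database lock, a slightly stricter final threshold, and about half a point of stated power. No additional patients or data are needed.

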3.2 Screening and eligibility assessment

Start of period: When a given patient is admitted to the hospital because unexplained COPD exacerbation.

End of period: Twenty-four hours after decision to admit to hospital.

Setting: Emergency Department.

e-CRF entries:

- Demographics: date of birth, gender
- Medical history
- Concomitant medication
- Physical examination: height, weight, heart rate, systolic blood pressure, temperature, respiratory rate, arterial oxyhemoglobin saturation
- Inclusion and exclusion criteria
- Laboratory tests: hemogram, biochemistry, and hemostasis
- Chest X-ray
- Informed consent

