- To clearly define all variables, end points/outcomes, parameters, thresholds used for the statistical analyses.
- To define strategies employed regarding missing data on end points and possibly on adjustment variables.
- To describe statistical methods performed during the analyses.
- To define the populations of patients used during the analyses.

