3.6 Subgroup analyses

Several analyses will be run by subgroups, as follows:

[figure not shown]
Subgroup	End point
Age <75 ≥75 years	Primary and secondary end points
Sex Women Men	Primary and secondary end points
COPD severity FEV ₁ ≥80% 50% ≤FEV ₁ <80% 30% ≤FEV ₁ <50% FEV ₁ <30%	Primary and secondary end points
Hospital size <300 beds ≥300 beds	Primary and secondary end points
Season	Primary and secondary end points

Autumn	
Winter	
Spring	
Summer	

FEV₁: volumen espiratorio máximo en el primer segundo.

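### The primary test is a valid chi-square that uses no patient-level prognostic covariates; a prespecified adjusted analysis could add about 1 to 5 points of power if age, sex and FEV1 explain 2–12% of outcome variance

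*SAP*

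**What the plan says.** SAP 3.5.2 sets the deciding test: "The primary efficacy and safety end points will be analyzed by means of a two-sided chi-square test of proportions". Protocol 2.10 is consistent with it: "The primary ITT analyses will be carried out by the chi square test on proportions, or the Fisher exact test". The abbreviated protocol also names a two-sided chi-square. Results are to be reported as relative risks with 95% confidence intervals.

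The next sentence of SAP 3.5.2 adds that the primary results will also be shown stratified by centre. It cites a paper on the analysis of trials with stratified randomization, but it names no method and does not make this the deciding analysis. Centre is the only stratification factor (SAP 2.3).

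Neither document plans a model that adjusts the primary end point for a patient characteristic. Among its objectives, SAP 1 lists: "To define strategies employed regarding missing data on end points and possibly on adjustment variables". No adjustment variable is then defined.

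The covariates appear elsewhere in the plan. The screening entries in Protocol 3.2 include "Demographics: date of birth, gender". Age, sex and FEV1 class are subgroup factors in SAP 3.6, each applied to "Primary and secondary end points".

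**The concern.** The primary end point combines death, symptomatic VTE and COPD readmission at 90 days. Age and severity of airflow obstruction plausibly predict at least death and readmission. A crude comparison leaves that predictable variation in the error term. It also leaves in the estimate whatever chance imbalance in age or FEV1 arises, since randomization does not stratify on either.

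Adjustment followed by standardisation estimates the same marginal relative risk that the SAP already reports, usually with a smaller standard error. At stake are some precision and a little power, in a design sized to reach almost exactly 80% and no more. The validity of the test is not at stake.

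**Working it through.** **Inputs from the documents.** SAP 2.2 gives the target: "clinically important 10% absolute reduction in the primary outcome (i.e., from 40% to 30%) with 80% power at 5% significance level". It also gives 355 per group, inflated to 373 for 5% loss. SAP 3.5.2 gives the level: "The alpha level of the two-sided test is set to 0.05". Allocation is 1:1.

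**Input assumed.** R², the share of outcome variance explained by the baseline covariates. No value is given in either document, so a range is shown.

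**Step 1: reproduce the plan's figure.** With p₁ = 0.40, p₂ = 0.30 and mean 0.35:

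n = [1.960 × √(2 × 0.35 × 0.65) + 0.842 × √(0.40 × 0.60 + 0.30 × 0.70)]² / 0.10²

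This gives 356 per group; the arcsine formula gives 355.4. The stated 355 reproduces. Inflation also holds to rounding: 355 × 1.05 = 372.75 and 355 / 0.95 = 373.7.

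**Step 2: power of the planned test.** Evaluable n is 373 × 0.95 = 354 per arm.

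Power = Φ{[0.10 × √354 − 1.960 × √0.455] / √0.45} = Φ(0.834) = 79.8%

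**Step 3: power with adjustment.** Adjustment multiplies the variance of the risk difference by about (1 − R²), so the effective n is 354 / (1 − R²).

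| Assumed R² | Effective n per arm | Power | Gain (points) | Equivalent extra patients per arm |
|---|---|---|---|---|
| 0 | 354 | 79.8% | – | – |
| 2% | 361.2 | 80.6% | 0.8 | 7 |
| 5% | 372.6 | 81.8% | 2.0 | 19 |
| 12% | 402.3 | 84.6% | 4.8 | 48 |

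**Step 4: check by simulation.** Logistic outcomes, three covariates, 355 per arm, 6,000 trials per setting, with logistic standardisation and an influence-function standard error:

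- R² about 2% (c-statistic about 0.58): 79.7% unadjusted, 80.9% adjusted.
- R² about 5% (about 0.63): 80.4% and 82.7%.
- R² about 11–12% (about 0.70): 79.9% and 84.8%.
- No effect (40% in both arms, R² about 5%): type I error 4.7% unadjusted, 4.9% adjusted.

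Monte Carlo error on each power is about √(0.8 × 0.2 / 6,000) = 0.5 points, so the simulation agrees with the formula. It confirms the gain for a given R². It says nothing about what R² is in this population.

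**The case against.** The strongest reply is that nothing here is wrong. A chi-square is valid in a 1:1 randomized trial, the protocol and SAP agree on it, and the sample size was built for it. Chance imbalance does not inflate its type I error. All of this stands.

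Four stronger readings are tempting, and the documents do not support them:

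- **That the plan loses a known 2 to 5 points of power.** This needs R² of about 5% to 12%, which no section supplies. At 2% the gain is under one point.
- **That the plan contains no adjustment at all.** A centre-stratified result is planned, although it is additional and uses no patient-level predictor.
- **That SAP 1 promises covariate adjustment.** Its wording is conditional and sits in a line about missing data.
- **That FEV1 is known to be recorded afresh before randomization.** The screening list in Protocol 3.2 names no spirometry. Protocol Table 1 speaks of a previous diagnosis, so values may be historical. SAP 7 anticipates patients whose COPD was not objectively confirmed. FEV1 is inferred to be available from the eligibility criterion and the planned subgroups.

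It can also be said that the design has a little margin. SAP 2.2 reports 3% loss at the interim; if that persisted, 373 × 0.97 = 362 per arm would be evaluable and power would be 80.7%. That is fair, and the margin is under one point.

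The most serious practical objection is timing. An interim analysis has already taken place in an open-label trial, so replacing the deciding test now could look data-driven. This does not remove the case for an adjusted analysis, but it bears on whether that analysis should decide the trial.

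**Conclusion.** The concern holds as a missed efficiency. The deciding test ignores age and sex, which are collected at baseline, and FEV1 class, which the trial's own subgroups require. If these explain 2% to 12% of outcome variance, power at 354 evaluable per arm would rise from 79.8% to about 80.6% to 84.6%, a gain of about 1 to 5 points without further recruitment.

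This rests on the assumed R², on the plan's 40% versus 30%, on a two-sided 0.05 test and on 5% loss. The direction of the gain is secure if the covariates are prognostic; its size cannot be settled from the documents. A reader should not infer that the planned test is invalid or that the sample size is wrong.

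**What to change.** Before database lock, and by people without sight of comparative data, prespecify in SAP 3.5.2 a logistic model with arm, centre, age (continuous), sex and FEV1 class. Standardise it over the randomized population to give the marginal relative risk and risk difference with robust 95% confidence intervals.

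- Include centre, because randomization is stratified by it. This also gives the planned centre-stratified result a defined method.
- Treat missing FEV1 as its own category so that no patient is dropped for a missing covariate, and state which pre-randomization value counts when spirometry is historical.
- Use the FEV1 class limits of SAP 3.6. Those in Protocol 2.10 leave a value of exactly 80% unassigned.
- State which analysis decides the trial: either the adjusted model, with the chi-square as its unadjusted companion, or, in view of the interim analysis already done, the chi-square, with the adjusted model as the named key supportive analysis.

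Align Protocol 2.10 and the abbreviated protocol, since both name the chi-square and a change to the SAP alone would put the documents in conflict.

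The cost is a wording change to both documents and a few lines of code. The covariates and the missing-FEV1 rule must be fixed in advance. No new data collection is needed if FEV1 is held for the subgroups as the plan implies.
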